Randomization takes place before birth or immediately after the birth of the child. The research assistant or investigator obtains the formula allocation code from the Data Management Unit (DMU) by completing the Randomization Form electronically. Subjects who meet the inclusion and do not meet exclusion criteria are randomized as follows: randomization in each strata will be within four blocks. Subjects will receive either the test formula, casein hydrolysate (Nutramigen™, Mead Johnson Nutritionals), not containing antigenic CM protein, or a CM protein containing control formula which has an addition (20 %) of Nutramigen, whenever breast milk is not available. Any subject requiring supplemental feeding prior to randomization (e.g. infants born at night or on weekends) is given banked breast milk or Nutramigen. The randomization code will be kept by the manufacturer and it will be opened when TRIGR study is completed.

Cord blood is obtained from newborn infants whenever possible or alternatively a heel prick is performed to obtain capillary blood as soon as possible after birth, at the latest at the age of 7 days. The blood sample is forwarded to the continental genotyping center and screening performed for the presence of the genotypes listed below indicating an increased genetic risk. Results are entered into the Central Data Base immediately when available (within 2 weeks after the sampling) and are sent by e-mail from DMU to the national coordinating centers and/or to the local study center in question and to the Study Monitors. Only subjects with these genotypes are included in the nutritional prevention trial; all other subjects are withdrawn from the study at that time; their parents are told that genetic screening suggests that their child does not fall into the increased genetic risk group for type 1 diabetes and they are appropriately thanked for their participation. It is emphasized that their child might still develop diabetes despite not meeting the eligibility criteria.

E. GENETIC SCREENING

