 - 2 hour venous plasma glucose ≥ 11.1 mmol/l = 200 mg/dl (2 hour venous blood glucose ≥ 10.0 mmol/l = 180 mg/dl) on two occasions.

Accordingly a second OGTT should be performed, if the first one is diabetic. There should be an interval of at least one week between these two OGTTs.

The diabetes-associated autoantibody data will be disclosed when the autoantibodies have been assayed after the 6-year visit, and the family will be informed by the Study Center as soon as the autoantibody results have become available.

I. METHODOLOGY TO BE APPLIED

Methodology for Genetic Screening

The procedures used for HLA-DQ typing were specifically developed for screening relevant DQB1 and DQA1 alleles (11, 12). EDTA treated cord blood is collected. Alternatively capillary blood is taken postnatally if cord blood is not available. The blood samples are sent by air mail or special delivery from the U.S. and Canadian centers to the tissue typing laboratory of Professor [name], University of Pittsburgh, PA, USA, and from the various European and other centers to the tissue typing laboratory of Dr. [name], University of Turku, Finland. According to experiences from the Pilot-2 study of the project (Finland, Sweden, Estonia and Hungary), the result of the genetic screening is available within 2 weeks to assess the eligibility of the infants. The results are entered into the Central Data Base immediately when available, and the Study Center is alerted by e-mail.

The polymorphic gene region is amplified in a microtiter format using biotinylated primers. The amplification product is subsequently transferred to streptavidin coated microtiter plates where it is bound by solid phase streptavidin. After denaturation the hybridization reaction is performed with a mixture of lanthanide (Europium, Samarium or Terbium) labeled sequence specific oligonucleotide

probes and specific hybridization signals detected by time-resolved fluorometry after repeated washes and the addition of enhancement solution.

Methodology for Autoantibodies

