We will use islet cell antibodies (ICA), insulin autoantibodies (IAA), antibodies to the 65 kD isoform of glutamic acid decarboxylase (GADA) and antibodies to the protein tyrosine phosphatase related IA-2 molecule (IA-2A) as humoral markers of β -cell autoimmunity. All autoantibody analyses will be performed in the laboratory of Professor [name], University of Helsinki. His laboratory has a long experience and acknowledged expertise in the analysis of diabetes-associated autoantibodies. The laboratory will pay particular attention to quality control procedures of the assays for autoantibodies. All samples are bar-coded, and the analyses will be performed on a blinded basis. Samples from the same individual will, however, be stored in such a way that they can be run in the same assay. Samples will be analyzed in the following assay rounds: the first including samples from the baseline visit (0 month visit) up to the 2-year visit, the second from the 3-year visit to the 6-year visit, and after the 6-year visit annually visit by visit. Possible assay drift over time will be monitored by analyzing blindly with each assay three standards (low, medium and high antibody levels) once a month. An assay drift exceeding 10% is considered unacceptable. The laboratory has completed a process of collecting optimal standards with sufficient volume for a period of 15 years.

ICA are analyzed with a standard immunofluorescence assay performed on sections of frozen human pancreas from a blood group O donor (13). Fluorescein-conjugated anti-human IgG (Sigma, St Louis, MO, USA) is used to detect ICA. All initially ICA-positive samples are re-tested to confirm antibody positivity. End-point dilution titers are identified and the results are expressed in Juvenile Diabetes Foundation (JDF) units relative to an international reference standard (14). The detection and cut-off limit is 2.5 JDF units. The sensitivity of this ICA assay was 100%, the specificity 98% the validity 98%, and the consistency 98% in the most relevant international standardization round.

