 - Investigators meeting at the end of the 5. year to evaluate the progress of the study
6. year
- Recruitment is completed
 - Clinical follow-up of the children and collection of the follow-up samples are continued
 - Continuation of the assays of immunological markers
 - Dietary advice and assessment, and monitoring of the implementation of the dietary intervention are completed
 - Monitoring of the implementation of the clinical follow-up continues
 - Analysis of the dietary data are continued
 - Investigators meeting to evaluate the progress of the study
7. year
- Clinical follow-up of the children and collection of the follow-up samples are continued
 - Monitoring of the implementation of the clinical follow-up continues
 - Continuation of the assays of immunological markers
 - Analysis of the dietary data are continued
 - Investigators meeting to evaluate the progress of the study
- 8.- 11. year
- Clinical follow-up of the children and collection of the follow-up samples are continued
 - Monitoring of the implementation of the clinical follow-up continues
 - Continuation of the assays of immunological markers
 - Investigators meeting to evaluate the progress of the study
12. year
- The last recruited child reaches the age of 6 years
 - Interim analysis of autoantibodies and clinical diabetes is performed
 - Clinical follow-up of the children and collection of the follow-up samples are continued
 - Monitoring of the implementation of the clinical follow-up continues
 - Continuation of the assays of immunological markers
 - Investigators meeting to evaluate the progress of the study
- 13.- 15. year
- Clinical follow-up of the children and collection of the follow-up samples are continued
 - Monitoring of the implementation of the clinical follow-up continues
 - Continuation of the assays of immunological markers
 - Investigators meeting to evaluate the progress of the study
16. year
- The last recruited child reaches the age of 10 years
 - Clinical follow-up of the children and collection of the follow-up samples are completed

- Monitoring of the implementation of the clinical follow-up is completed
- The randomization code is opened

17. year

- The assays of immunological markers are completed
- Final analysis of autoantibodies and clinical diabetes is performed
- Investigators meeting at the end of the study

P. PUBLICATION POLICY

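### The timetable opens the randomisation code in year 16, before the immunological-marker assays finish in year 17, and nothing requires complete or locked data first

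*Combined protocol and SAP*

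**What the plan says.** Section O sets out the work year by year.

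- Under year 16, the last child turns 10, "Clinical follow-up of the children and collection of the follow-up samples are completed", monitoring of follow-up ends, and "The randomization code is opened".
- Under year 17 come "The assays of immunological markers are completed", "Final analysis of autoantibodies and clinical diabetes is performed" and "Investigators meeting at the end of the study".

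Section D (Subject Allocation) leaves the code with the manufacturer and says "it will be opened when TRIGR study is completed". It names no year and no preceding event.

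Section I (Methodology for Autoantibodies) says of the laboratory: "All samples are bar-coded, and the analyses will be performed on a blinded basis". Sera up to the 6-year visit are run in two rounds. Later sera are run once a year, one visit at a time.

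Section H (Outcome Assessment) sets the first-phase outcome at age 6 (autoantibodies and/or diabetes) and the second-phase outcome at age 10 (diabetes). Section L plans a repeated-measures antibody analysis with no upper age. The analysis text after Table 1 in Section B makes covariate adjustment, and the choice between stratification and regression, depend on the baseline differences found.

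**The concern.** In a double-blind trial the allocation key is normally released only when the outcome data are final and the analysis is fixed. Here the plan's own order releases it in the year before the marker assays are finished, and no other section supplies the missing condition.

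Two things are at stake. First, the longitudinal antibody data set and the year 17 antibody analysis would include results produced or cleaned after allocation is known at trial level. Second, Section B leaves adjustment to be settled from the data. If the key is already open and no lock is required, that choice can be made with allocation known. The second point touches the diabetes comparison as well as the antibody comparison, and bar-coding in the laboratory does not address it.

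The four-colour scheme in Section F makes the release complete. Each child keeps one colour, and families and centers know it, so disclosing which colours are test and which are control reveals every allocation at once.

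**Working it through.** The plan states no figure to reproduce, so the check sets the sections side by side.

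1. **Timetable.** Section O completes recruitment in year 6. The last child is then 6 in year 6 + 6 = 12 and 10 in year 6 + 10 = 16. Both agree with the entries for those years, so the year labels are coherent and can be read as an order of events.

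2. **Order.** Code opening is in year 16. Assay completion, final analysis and the end-of-study meeting are in year 17. Opening therefore precedes assay completion.

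3. **Length of the gap.** Entries are in whole years. From the labels alone the gap could be anything from days (end of 16 to start of 17) to just under two years (start of 16 to end of 17). The order is certain; the interval is not.

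4. **Section D against Section O.** If study completion means the end of follow-up, Section D agrees with year 16. If it means the end-of-study meeting, it points to year 17 and the two sections disagree. The text does not settle which is meant. On either reading no section asks for finished assays, final outcome classification or a database lock first.

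5. **Which results can be late.** All 6-year sera are collected by year 12 and belong to the second assay round, so they should not be among those open in years 16 and 17. Later sera are assayed annually. Section H keeps children in follow-up until the youngest is 10 and the oldest 14, so the last batch comes mainly from children of about 10 and over.

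6. **Which analyses use them.** The first-phase outcome is fixed at age 6. The second-phase outcome rests on symptoms, glucose and the OGTT, not on these assays. That leaves the Section L longitudinal antibody analysis, which has no age limit, and the autoantibody part of the year 17 final analysis.

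7. **Where judgement enters.** Re-runs follow fixed rules: IAA above the 95th centile, GADA and IA-2A between the 97.5th and 99.5th percentiles, and every initially positive ICA sample. IAA, GADA and IA-2A are counter readings against set cut-offs. ICA is an immunofluorescence reading on tissue sections with an end-point titre, so it has the most room for judgement. Outside the laboratory, judgement enters through data cleaning and the adjustment choices in Section B.

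**The case against.** The strongest reply is that little is really exposed. Several parts of it stand.

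- **Laboratory blind.** A reader might infer that the last assays are run unblinded. The documents do not support this. Section I requires bar-coded samples and blinded assays with no exception after code opening, and nothing gives the laboratory the colour or the allocation. Section I does not, however, say how that blind is kept once the key is out.
- **Diabetes confirmations.** The last visit includes an OGTT in every child, and Section H says "Accordingly a second OGTT should be performed, if the first one is diabetic", at least a week later. A reader might infer that confirmations are pending when the code is opened. Section O lists clinical follow-up as completed in year 16, ahead of the code-opening line, and confirmatory tests can fairly be counted as follow-up. Pending confirmations are therefore speculative.
- **Number of results.** One could take 2,032 × 0.8 = 1,626 last sera after 20% drop-out, times four antibodies, or about 6,500 results. That assumes every last serum is unassayed at code opening. No section says so. The year 17 entry may cover a small remainder, and the term immunological markers is not defined there. The count should not be used.
- **Analysis after opening.** Comparing arms requires the allocation, so a final analysis in year 17 with the code open is no fault in itself.
- **Section D.** Study completion can be read as the end of follow-up, so this is an ambiguity rather than a proven contradiction.
- **Data-driven adjustment.** This is also a separate pre-specification issue, and moving a timetable line alone would not cure it. The order still matters, because it decides whether those choices can be made with allocation known.

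What the reply does not remove is the order itself and the absence of any condition on opening the code.

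**Conclusion.** The point holds in limited form. The planned sequence ends the trial-level blind before the marker assays are complete, and without requiring final outcome classification or a locked database and model. The exposure is confined to late annual autoantibody results, the data cleaning around them, and the adjustment choices still open under Section B.

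The age-6 antibody outcome is not affected, on the assumption that the second assay round is finished well before year 16. The laboratory should remain blinded as long as Section I is followed. Neither the number of exposed results nor the direction or size of any bias can be derived from the documents, and no sample size, power or error rate changes. Confidence is high on the order of events and lower on its consequences. Severity is minor to moderate; the case for acting rests mainly on how cheap the correction is.

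**What to change.** 1. In Section O, move the code-opening entry from year 16 to year 17. Place it after the entry on completion of the assays and before the final analysis. Make it conditional on final outcome classification and on locking the database and the analysis model.
2. In Section D, say that, apart from early opening under Section M, the code is opened only after all outcome assays are complete and the database is locked.
3. In Section I, state that the autoantibody laboratory stays blinded until its assays end, including if the code is opened early under Section M, which allows opening while follow-up continues.

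The cost is one timetable line moved and two clauses added. The final analysis is already in year 17, so it is not delayed. Allocation is disclosed somewhat later: by up to about a year if the present plan means opening at the close of year 16 follow-up, though the whole-year entries do not fix the interval exactly.
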